## 4 STUDY DESIGN

### 4.1 OVERALL DESIGN

Allocation: Randomized 1:1 RELIEF stent vs. DJ Stent

Endpoint Classification: Comparison Study

Intervention Model: Two Group Assignment

Masking: Open Label

Primary Purpose: Treatment

Patients will undergo their scheduled ureteroscopy with laser lithotripsy and ureteral stent placement per standard of care methods.

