### 2.3.2 KNOWN POTENTIAL BENEFITS

There is potential direct benefit for the patients assigned to the RELIEF stent group as we suspect it will provide relief from discomfort during recovery after ureteroscopy. The knowledge to be gained from this research is whether the Relief stent reduces urinary reflux and decreases postoperative pain and discomfort for patients who undergo kidney stone surgery and stent placement. If the Relief stent provides improvement in symptoms, this will improve patient care and comfort.

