**Study Endpoints:****1- Primary effectiveness endpoint:**

- Study success defined as adequate short-term drainage defined as the presence of the stent in the ureter and the lack of surgical or other intervention to treat symptoms associated with the stent itself on the stented side during the first 48 hours [Day 0-2] following placement.
- [Note: In some cases, the ureteral stent may not be sufficient to relieve pain (not associated with stent specifically) and alternative surgical treatment may be warranted. In these cases, patient data will be captured but non-device related cause captured as reason for subject stenting termination.]
- Assessment of retrograde urine reflux after placement of the ureteral stent, as determined by the visualization of urine in the distal ureter to the kidney using cystography after contrast gravity-filling of the bladder and assigning a urinary reflux grade based on:
  - Grade I: urine refluxes into the ureter only.
  - Grade II: urine refluxes into the ureter and up to the kidney without dilation.

- Grade III: urine refluxes into the ureter and kidney and causes mild dilation.
- Grade IV: urine refluxes into ureter and kidney and causes dilation without twisting of the ureter.
- Grade V: urine refluxes into ureter and kidney and causes significant dilation with twisting of the ureter.

- Visualization of distal coil in bladder, after stent placement. Document placement using a cystoscope.

2- Primary safety endpoint:  
Assessment of pain or irritative symptoms (incidence, severity) attributed to the ureteral stent as well as unplanned return visits to ED, OR, or clinic.

3- Secondary endpoint:

- USSQ Scale (Ureteral Stent Symptoms Questionnaire) [Time Frame: Day 3 as endpoint]
- Unplanned hospital visits or doctor visits related to the stent
- Medication use endpoint:
  - Physicians can prescribe standard medications such as alpha blocker (Tamsulosin), Anticholinergic (Oxybutynin), phenazopyridine (Pyridium), ibuprofen and Tylenol prn pain for the duration of the stent plus 1 day (post stent removal) (Document on CRF)
  - Requests for “breakthrough” pain medication (narcotics) would be at the request of the patient post procedure (not to be given as a standard dose). (Document on CRF)
  - Patients to keep medication diary in situations where patients are not taking medications as prescribed

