#### Day 0 (Stent Placement)

- Patients will be randomized to one of two study groups (Relief stent vs DJ stent)
- Medical charts will be reviewed and medications will be reviewed prior to surgery
- Stent will be placed per standard of care
- A intraoperative photo of the stent will be taken to confirm placement

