## 6.3 MEASURES TO MINIMIZE BIAS: RANDOMIZATION AND BLINDING

Patients will be randomized to receive either the Relief stent or the standard ureteral stent. The randomization sequence will be computer-generated, and patients will be randomly allocated based on this sequence.

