## 6.4 STUDY INTERVENTION COMPLIANCE

There will be three questionnaires completed by subjects at multiple different timepoints which will ensure study intervention compliance.

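### No one is masked, so patient expectation can influence the Day 3 USSQ and the other symptom outcomes; masking the participant through Day 3 would be a cheap improvement

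*Combined protocol and SAP*

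**What the plan says.** Section 4.1 gives the masking status as "Masking: Open Label", with no exception for the patient, the staff who contact the patient, or the reader of the cystogram. Section 6.3 is headed as covering blinding, but its content is randomization only: "The randomization sequence will be computer-generated, and patients will be randomly allocated based on this sequence".

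Allocation happens on the day of surgery (section 4.1, Day 0): "Patients will be randomized to one of two study groups (Relief stent vs DJ stent". The stent is placed the same day.

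Three outcomes depend at least partly on patient report or request (section 3):

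- The secondary symptom endpoint: "USSQ Scale (Ureteral Stent Symptoms Questionnaire) [Time Frame: Day 3 as endpoint". Section 6.4 confirms who fills in the forms: "There will be three questionnaires completed by subjects at multiple different timepoints".
- The safety outcome that the plan ranks as primary: "Assessment of pain or irritative symptoms (incidence, severity) attributed to the ureteral stent as well as unplanned return visits to ED, OR, or clinic".
- Medication use compared between arms, where narcotics for breakthrough pain are given when the patient asks for them.

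The direction of the investigators' expectation is stated in section 2.3.2: "There is potential direct benefit for the patients assigned to the RELIEF stent group as we suspect it will provide relief from discomfort".

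Section 9.4.3 compares USSQ scores between arms by Mann-Whitney or independent t-test, without adjustment. Section 8.4.3 has surgical results passed on to the patient or a family member in the usual way and does not exclude the type of stent.

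**The concern.** Fewer irritative symptoms is one of the two added benefits hypothesized in section 3, and section 2.1 presents it as the consequence of less reflux. It is also the benefit that patients would notice. If patients know they received a device called RELIEF that is expected to ease discomfort, they may report fewer symptoms or ask for less pain medication even if the stents are equivalent. Such a shift points in one direction, and a larger sample does not remove it. An unadjusted comparison of scores cannot tell it apart from a device effect.

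Baseline adjustment would not solve this, because the expectation arises after allocation. As scheduled there is also no baseline to adjust for. The objectives call for a USSQ before placement, but the Schedule of Activities and the follow-up list in section 4.1 start at Day 1.

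**Working it through.** **1. The plan's own figure.** Section 9.2 gives N = 50, w = 0.4, alpha 0.05 and power 80%. With a 1-df chi-square test the noncentrality is N × w² = 50 × 0.16 = 8, and the power is 0.807. The stated figure reproduces. It applies to reflux incidence; the USSQ has no power calculation.

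**2. Is masking provided anywhere?** Section 4.1 says open label, and section 6.3 adds only the sequence. Section 2.3.1 says patients cannot choose their stent, which does not conceal the one they receive. No section masks the patient, the interviewer or the cystogram reader.

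**3. Is masking through Day 3 compatible with the schedule?** Randomization and placement are both on Day 0, the stent is internal, and the Day 3 contact is a phone call. The follow-up text in section 4.1 puts removal at Day 7-10, after the Day 3 score. In the Schedule of Activities, as extracted, the removal entry sits under Day 3. The column heading and the follow-up text say otherwise, so this may be an extraction fault.

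**4. How much could an expectation shift matter?** The documents give no USSQ SD, target difference or bias size, so the shift b (in SD units) is an assumption.

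- Inputs: n = 25 per arm (section 9.2), t-test (one of the two tests allowed in section 9.4.3), two-sided alpha 0.05 (the plan gives 0.05; two-sided is assumed), true effect zero.
- Degrees of freedom: 2 × 25 − 2 = 48.
- Noncentrality: b × √(n/2) = b × √12.5 = b × 3.536.
- Smallest observed difference that reaches significance: 0.57 SD.
- Chance of a significant result favouring RELIEF: the probability that a noncentral t variable with 48 df exceeds the upper 2.5% point of the central t.

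| Assumed shift b (SD) | Noncentrality | Significant, favouring RELIEF | Significant, either direction |
|---|---|---|---|
| 0 | 0 | 2.5% | 5.0% |
| 0.1 | 0.354 | 5.3% | 6.4% |
| 0.2 | 0.707 | 10.3% | 10.7% |
| 0.3 | 1.061 | 17.9% | 18.0% |
| 0.5 | 1.768 | 41.0% | 41.0% |

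The concern is a false benefit for RELIEF, so the third column is the relevant one, to be read against 2.5%.

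**The case against.** Open label is a disclosed design choice, and the surgeon cannot be masked. The Day 3 USSQ is a secondary endpoint. The powered endpoint is read from a cystogram, where patient belief is not the main route of bias. This stands, and it confines the point to the symptom conclusions. It does not remove the point, because pain or irritative symptoms are also the primary safety endpoint.

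The size of the bias is unknown. This also stands: at 0.1 SD the chance of a false RELIEF benefit is only about 5%, and the 41% rests on the largest shift shown. The figures are for the t-test; the plan also allows Mann-Whitney.

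Three stronger readings are tempting, and the documents do not support them:

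- *Patients are told which stent they have, or that RELIEF should hurt less.* Open label permits disclosure but does not show what patients are told or when. The consent pages are not available, and the expectation in section 2.3.2 is the investigators' own statement.
- *The symptom outcomes are wholly a product of belief.* Physicians prescribe the standard medications, and unplanned visits also reflect clinical events. Influenced by expectation is as far as the text goes.
- *The symptom result would be uninterpretable.* Reflux is imaged in the same patients, which gives partial evidence on the proposed mechanism, although it does not measure how much of a symptom difference is due to expectation.

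Finally, masking may leak, through the operative note or through the usual post-operative conversation under section 8.4.3. That is a reason to write the change carefully. Partial masking at Day 3 still reduces the bias.

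**Conclusion.** The concern holds for the symptom conclusions: the Day 3 USSQ, the symptom-based primary safety endpoint and patient-requested narcotic use. Nobody is masked, the investigators' expectation has a stated direction, and the planned tests cannot remove its effect. It does not carry over to the powered reflux comparison, for which patient expectation is not the main route of bias.

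The size cannot be derived from the documents. The illustrated range, about 5% to 41% for shifts of 0.1 to 0.5 SD, assumes no true effect, 25 evaluable patients per arm and a two-sided 5% t-test. It shows what a bias of that size would do, not that such a bias will occur. Participant masking through Day 3 fits the schedule, so this is a cheap and worthwhile improvement. It is not a defect that invalidates the trial.

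**What to change.** - **Section 4.1:** replace the masking entry with: participant masked to stent type at least through the Day 3 USSQ, and where possible through the last USSQ; surgeons unmasked. State the same in section 6.3.
- **Consent:** say that the stent is assigned at random and that the assigned type will not be disclosed until that point.
- **Section 8.4.3:** specify that reports of the surgical outcome to the patient or family do not name the stent type during the masked period.
- **Day 1 and Day 3 contacts:** ask the staff making them not to name the stent.
- **Unmasking:** allow it on clinical need or at the patient's request, and record the date so that leakage is visible at analysis.
- **If masking is not adopted:** report the symptom results explicitly as open-label.

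The cost is protocol and consent wording, with no added visits, patients or procedures. The downsides are that staff must avoid naming the stent, some patients may learn it from the operative note, and an unmasking route has to be kept. This change does not mask the cystogram reader, which is a separate matter for the reflux endpoint.

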#### Screening/Enrollment:

- Patients will be screened for eligibility
- If eligible, patients will be enrolled in the study through signing of the Informed Consent Form
- Medical charts will be reviewed, demographics will be collected, and medications will be reviewed prior to surgery

#### Day 0 (Stent Placement)

- Patients will be randomized to one of two study groups (Relief stent vs DJ stent)
- Medical charts will be reviewed and medications will be reviewed prior to surgery
- Stent will be placed per standard of care
- A intraoperative photo of the stent will be taken to confirm placement

#### Post-stent Follow-Up:

- Post-operatively complete Ureteral Stent Satisfaction Questionnaire (USSQ) surveys at day 1, day 3, day of stent removal, and 2 days post stent removal (note day of removal) (between 7-10 days in normal practice (even up to 14 days):
- Medications will be tracked on the CRF at day 1, day 3, day of stent removal, and 2 days post stent removal
- Day 1 (12-30 hours after stenting procedure), subject will be evaluated by study personnel for acceptable procedural outcome.
- Document any unplanned hospital visits or doctor visits related to the stent  
Day 1, Day 3, Day of stent removal (i.e., Day 7-10), and 2 days post stent removal, subject will be evaluated by study personnel for ongoing tolerability and stent performance (e.g., drainage) in person or by phone.
- Direct or remote evaluation will be documented. If unusual levels of pain or other potentially serious complications are suspected, the subject will be brought in for Clinician evaluation.

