### 8.3.3.2 RELATIONSHIP TO STUDY INTERVENTION

All adverse events (AEs) must have their relationship to study intervention assessed by the clinician who examines and evaluates the participant based on temporal relationship and his/her clinical judgment. The degree of certainty about causality will be graded using the categories below. In a clinical trial, the study product must always be suspect.

- **Definitely Related** – There is clear evidence to suggest a causal relationship, and other possible contributing factors can be ruled out. The clinical event, including an abnormal laboratory test result, occurs in a plausible time relationship to study intervention administration and cannot be explained by concurrent disease or other drugs or chemicals. The response to withdrawal of the study intervention (DE challenge) should be clinically plausible. The event must be pharmacologically or phenomenologically definitive, with use of a satisfactory rechallenge procedure if necessary.
- **Probably Related** – There is evidence to suggest a causal relationship, and the influence of other factors is unlikely. The clinical event, including an abnormal laboratory test result, occurs within a reasonable time after administration of the study intervention, is unlikely to be attributed to concurrent disease or other drugs or chemicals, and follows a clinically reasonable response on withdrawal (dechallenge). Rechallenge information is not required to fulfill this definition.
- **Potentially Related** – There is some evidence to suggest a causal relationship (e.g., the event occurred within a reasonable time after administration of the trial medication). However, other factors may have contributed to the event (e.g., the participant's clinical condition, other concomitant events). Although an AE may rate only as "possibly related" soon after discovery, it can be flagged as requiring more information and later be upgraded to "probably related" or "definitely related", as appropriate.
- **Unlikely to be related** – A clinical event, including an abnormal laboratory test result, whose temporal relationship to study intervention administration makes a causal relationship improbable (e.g., the event did not occur within a reasonable time after administration of the study intervention) and in which other drugs or chemicals or underlying disease provides plausible explanations (e.g., the participant's clinical condition, other concomitant treatments).

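### Unplanned visits: the safety endpoint has no cause limit, but the follow-up instruction and the secondary endpoint cover only stent-related visits, with no rule for that judgement in an open-label trial

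*Combined protocol and SAP*

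**What the plan says.** Two scopes for unplanned visits appear in the combined protocol and SAP.

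- **No cause limit.** The primary safety endpoint in section 3 reads "Assessment of pain or irritative symptoms (incidence, severity) attributed to the ureteral stent as well as unplanned return visits to ED, OR, or clinic". The phrase about attribution qualifies the symptoms; the visits stand without a qualifier. The first secondary objective in section 3 treats visits the same way.
- **Related only.** The secondary endpoint, in section 3 and in the synopsis (1.1), is "Unplanned hospital visits or doctor visits related to the stent". The visit-specific collection instruction, under Post-stent Follow-Up in section 4.1, has the same limit: "Document any unplanned hospital visits or doctor visits related to the stent".

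Section 4.1 states "Masking: Open Label", and section 6.3 describes randomization but no blinding. At follow-up the "subject will be evaluated by study personnel for ongoing tolerability and stent performance (e.g., drainage) in person or by phone". The documents do not say who decides whether a visit is stent-related, or by what criteria. The only relatedness rule is for adverse events (8.3.3.2): "All adverse events (AEs) must have their relationship to study intervention assessed by the clinician who examines and evaluates the participant".

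A second route collects visits. Sections 2.3.3 and 8.2 require a standard form for every adverse event that lists the office, emergency and hospital visits it needed. Section 8.3.4 requires all adverse events to be documented whatever their presumed cause.

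**The concern.** Staff who follow section 4.1 as written need not record a visit they consider unrelated to the stent, yet the primary safety endpoint needs that visit. The collection step is narrower than the endpoint it serves.

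The related-only endpoint has a further weakness. Patients have stones or strictures and undergo ureteroscopy with laser lithotripsy, and section 3 itself notes that pain may not come from the stent. Deciding what caused a return visit is therefore a matter of judgement. With open-label treatment, no criteria and no blinded assessor, that judgement can differ by arm. The investigators' expectation is on record; section 2.3.2 says of RELIEF that "we suspect it will provide relief from discomfort during recovery after ureteroscopy". At stake are a fair comparison on the secondary visit endpoint and a complete visit count for safety.

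**Working it through.** **1. The plan's own figure.** Sections 4.2 and 9.2 give 80% power with 50 patients, w = 0.4 and alpha 0.05. The noncentrality is N × w² = 50 × 0.16 = 8; with 1 degree of freedom, power is 0.807. The figure reproduces, but it concerns reflux incidence. The documents give no visit rate and no attribution share, so every visit figure below is an assumption.

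**2. The mechanism.** Let q be the true risk of any unplanned visit, equal in both arms, and let a be the share of visiting patients whose visit is labelled stent-related.

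- Apparent risk in an arm = q × a.
- Apparent risk ratio = (q × a for RELIEF) / (q × a for DJ) = ratio of the two shares; q cancels.
- Shares 0.50 and 0.90: 0.50/0.90 = 0.56. With q = 0.20, the apparent risks are 0.10 and 0.18.
- Shares 0.60 and 0.90: 0.60/0.90 = 0.67. With q = 0.20, they are 0.12 and 0.18.
- Shares 0.80 and 0.80: ratio 1.0. Incomplete but equal attribution does not bias the ratio.

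**3. How often this would mislead at 25 per arm.** This is an exact binomial enumeration with two-sided tests at 0.05. No test is planned for visits, so the chi-square and Fisher tests named in section 9.4 for categorical variables are borrowed. Cells show the chance of a significant result favouring RELIEF (chi-square / Fisher) when there is no true difference.

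| True risk, both arms | All visits counted | Shares 60% vs 90% | Shares 50% vs 90% | RELIEF count lower, 50% vs 90% |
|---|---|---|---|---|
| 10% | 2.4% / 0.4% | 4.6% / 0.6% | 5.9% / 0.8% | 61% |
| 20% | 2.7% / 1.1% | 9.0% / 3.9% | 13.0% / 5.8% | 73% |
| 30% | 2.7% / 1.1% | 12.1% / 6.1% | 18.7% / 10.3% | 81% |
| 40% | 3.0% / 1.5% | 15.6% / 8.7% | 25.0% / 14.9% | 87% |

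With all visits counted, RELIEF has the lower count by chance in 41% to 44% of trials over the same range.

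**4. How much relabelling a significant result needs.** Suppose 8 patients per arm have visits and all 8 DJ patients are counted. Then 7 of the 8 RELIEF patients must be labelled unrelated for Fisher p < 0.05 (1 vs 8, p = 0.023). With 6 per arm, all 6 must be (0 vs 6, p = 0.022). The distortion therefore falls mainly on the point estimate.

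**5. What the adverse event route leaves uncovered.**

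- A visit without a recorded adverse event has no form. Under section 8.3.4, a condition present at screening is baseline unless it worsens, so a return for unchanged stone pain could fall here and also be judged unrelated under section 4.1.
- The form is filed per event, so one visit prompted by two events could be counted twice.
- Section 9.4.4 compares adverse events, not visits, and section 9.4.3 covers only the symptom questionnaire. No planned analysis rebuilds an all-visit count.

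**The case against.** The strongest reply is that the plan already captures most of these visits. Section 8.3.1 defines adverse events without regard to cause, section 8.3.4 has them asked about at each study visit, and the schedule in section 1.3 runs that review from Day 0 to 2 days after removal. A return for new flank pain, fever or hematuria should generate a form even if judged unrelated. This stands for visits tied to an adverse event, and narrows the gap to those without one.

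It can also be said that an all-cause safety measure and a narrower device-related secondary measure may coexist. That is fair: two scopes are not in themselves a contradiction. What remains is that the visit-specific instruction serves only the narrower one.

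A reader might infer more than the documents support:

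- *That unblinded staff are named as judges of relatedness.* They are not; this is a reasonable inference from the open-label design and from sections 4.1 and 8.3.3.2.
- *That attribution will favour RELIEF.* Section 2.3.2 makes that direction plausible, but nothing shows its direction or size.
- *That the all-visit safety count must be short in the same direction.* The adverse event forms prevent that conclusion.

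Nor would all-cause counting remove every bias. Section 4.1 has staff bring patients in when they suspect unusual pain, and patients are not stated to be masked. Either can affect whether a visit occurs.

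**Conclusion.** The point holds in a limited form. The visit instruction is narrower than the primary safety endpoint, and the related-only secondary endpoint depends on a judgement with no criteria or blinded assessor. Differential attribution could bias that comparison. Under the assumed 20% risk and 50% versus 90% labelling, equal arms would appear as 10% versus 18%, and a falsely favourable significant result would rise from 2.7% to 13.0% (chi-square) or from 1.1% to 5.8% (Fisher). These figures illustrate the mechanism and are not estimates for this trial. The all-visit count is only partly at risk. No test is planned for visits, and the powered reflux endpoint is untouched. The change is still worth making because visits not recorded during follow-up may not be recoverable later.

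**What to change.** - **Section 4.1, Post-stent Follow-Up, and the CRF:** record every unplanned emergency department, operating room, hospital or clinic visit from placement to 2 days after removal, with date and reason, whatever the cause.
- **Section 3, primary safety endpoint, and section 9.4.4:** make the all-cause count the between-arm comparison, as any visit (yes/no) and number of visits.
- **Sections 1.1 and 3, secondary endpoint:** report stent-related visits as a supportive, descriptive subset. Written criteria and a reviewer unaware of the arm would strengthen it.

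The cost is wording in a few places and a few CRF fields. Some unrelated visits will add noise to both arms, and bias from unblinded staff or patients prompting visits will remain.
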